3. STUDY DESIGN

This is an open label, block randomised (10 in each block), mixed method (quantitative and qualitative) study to be conducted for a period of up to 16 weeks

Children aged between 6-16 years with asthma attending the paediatric respiratory difficult asthma clinic will be recruited into the study and randomly allocated to one of three arms using block randomisation matched for age and size of group. Children will be assigned to trial one of the following four NEMD's to be tested:

1. Block 1 (10): Smartinhaler Plus™ (Adherium, New Zealand)
 - This measures inhalation usually flow sensors and is the next generation of a currently commercially available EMD
2. Block 2a (5) : Flo-Tone (Clement Clarke, UK) plus Rafi-tone, acoustic enabled Smartphone App (clin-e-cal, UK) for children aged 6 – 11 years
 - The Flo-Tone attaches to an MDI and makes a sound when the inhaler is used correctly. Rafi-tone is a Smartphone App that detects the sound and activates a game. The game is aimed at younger children and therefore children aged 6 – 11 years will be randomised to this block.
- Block 2b (5) : Inhaler Compliance Assessment (INCA™) device (INCA, Ireland)
 - This is an audio recording device which attaches to a Diskus dry powder inhaler. Analysis of the digital audio recordings enables objective assessment of inhaler use and technique. As it can only be used with a Diskus only children ≥ 12 years will be randomised to this block
3. Block 3: Video and Remote Directly Observed treatment (rDOT)
 - Children are filmed on a Smartphone using their inhaler. The clip is then automatically uploaded via a Smartphone App (Continga, UK) and reviewed by a Clinical Nurse Specialist to ensure inhaler technique is correct.

Recruitment

30 children will be recruited into the study; 10 per block (5 per block aged 6-11 years and 5 aged 12-16 years)

Visit 1: Novel electronic monitoring device (NEMD) issued

Routine clinical care assessments will be carried out at the end of the study period as below, including asthma control test (ACT) or the childhood asthma control test (cACT), exhaled nitric oxide (FeNO) and spirometry (FEV1 and BDR) .

Patient/parent/Carer will be invited to take part in the study.

Information regarding the study and its objectives will be communicated to the Patient/parent/carer in both oral and written form using patient information leaflets.

All children will be issued with a novel electronic monitoring device which will be attached to the child's usual inhaler or require an app on their mobile phone as described above. Parents and children will be provided information and advice on the use of the novel electronic monitoring device and asked to conduct up to 16 weeks of home monitoring using their allocated NEMD on their first visit.

Information on how to contact the team in case of any problems will be related to the participant in both oral and written form.

The data will be stored electronically and downloaded at the next clinic visit.

Contact by telephone will be made at day 7-14 to ensure that the device is working and to answer any other queries then at week 6-7 to determine if the device is being used appropriately and to answer any related questions.

Week 1 - for the rDOT arm, adherence data will be downloaded to check for consistencies in inhaler technique. If inhaler technique is inaccurate, the participants will be called by the respiratory nurse specialists to advise on correct technique. This will be documented as part of the data collection.

Week 4 – All devices, adherence data will be downloaded and checked to ensure that the devices are working correctly.

Visit 2: up to 16 weeks of adherence data collection

Routine clinical care assessments will be carried out at the end of the study period as below, including asthma control test (ACT) or the childhood asthma control test (cACT), exhaled nitric oxide and spirometry (FEV1 and BDR) .

Adherence data will be downloaded at the end of the study period and stored electronically.

Visit 3: Focus group or one to one interviews

The participants and their carers will be invited to a face to face focus group interview, or a one to one interview, depending on their availability at the end of the study period. The focus group and one to one interviews will utilise a semi structured questionnaire, to provide qualitative feedback on the acceptability and usability of the devices.

A separate focus group meeting will also be conducted with the paediatric respiratory nurses who are part of the MDT to assess their views on the devices used as they routinely provided all asthma devices and are also involved in downloading data from other devices that we would use as part of routine care (smart-inhaler). They will also be consented to take part in the study

Where possible a second researcher from University College London (UCL), [name] will sit in the focus groups discussion and interviews to ensure there is no bias.

The conversations from the focus group and one to one interviews will be transcribed and coded into themes. We will utilise an external company for transcribing the conversations called 1st Class. <https://www.1stclass.uk.com/>

Analysis

Qualitative:

The focus group and one to one interviews will be audio recorded, transcribed and put into themes to conduct an inductive thematic analysis. 25% of the transcripts (8) will be double coded by an independent researcher from UCL, [name], experienced in qualitative research to ensure that the correct themes have been used and to ensure that there is no bias.

The focus group and one to one interviews will be used to assess the usability and acceptability of the devices

Quantitative:

[figure not shown]
The amount of usable data from each device will be quantified and compared.

This will provide data on the perceived accuracy of the device.

The quantitative and qualitative results will be amalgamated and an evidence report prepared to assess the feasibility of each device.

An expert panel will be convened to select the most appropriate device to take forward to a larger randomised controlled trial to assess the impact of the device on adherence in children with asthma.

REFERENCE DIAGRAM

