4.2 INCLUSION CRITERIA

A child will be included in the study if the following criteria applies:

- Informed consent obtained from parents/guardian/adolescents and/or assent from the child.
- Children aged between 6-16 years with a diagnosis of asthma attending the Royal Brompton and Harefield Difficult asthma clinic.
- Children on inhaled corticosteroids
- Parents/ young person has a mobile phone which can download apps
- Paediatric respiratory nurses working in the difficult asthma team at Royal Brompton Hospital.

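### INCA needs a Diskus but its block is restricted by age alone, so a child of 12 or over could be allocated a device that does not fit the usual inhaler

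*Combined protocol and SAP*

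**What the plan says.** Section 3 (Study Design) allocates 30 children in blocks of 10. Block 2 is split into 5 children on Flo-Tone with the Rafi-tone app (2a, ages 6-11) and 5 on INCA (2b, ages 12 and over). Randomisation is matched on age and group size.

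On inhaler type, the device descriptions in section 3 say:

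- **INCA (2b):** "This is an audio recording device which attaches to a Diskus dry powder inhaler", and "As it can only be used with a Diskus only children ≥ 12 years will be randomised to this block".
- **Flo-Tone (2a):** "The Flo-Tone attaches to an MDI and makes a sound when the inhaler is used correctly".
- **Smartinhaler Plus (Block 1):** no inhaler type is named. The text is "This measures inhalation usually flow sensors and is the next generation of a currently commercially available EMD".
- **rDOT (Block 3):** no inhaler type is named. "Children are filmed on a Smartphone using their inhaler".

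Under Visit 1, the device is to be "attached to the child's usual inhaler or require an app on their mobile phone", with a reference back to the device descriptions.

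The treatment criterion in 4.2 is "Children on inhaled corticosteroids", and 4.3 excludes children not on them. Neither section mentions inhaler type, although 4.2 does require a phone that can run apps. The table in section 5 records drug history at Visit 1, which is also the visit at which the device is issued.

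**The concern.** The plan recognises the Diskus limit and answers it with an age rule, but being 12 or older does not make a child a Diskus user. If Visit 1 is followed and the device goes on the usual inhaler, an eligible child in Block 2b may be unable to use it. The protocol does not say what happens next, and three outcomes are possible:

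- The child drops out. One child is 1/5 = 20% of the evidence on that device. Under 4.4, data from a child who withdraws without more than 8 weeks collected are not used, so a failure to fit could leave no trace in that device's results.
- The child moves to another device, and the group is no longer the one randomised.
- The child's inhaler is changed to suit the device. Views on usability and acceptability, and the asthma control measures, then reflect a new inhaler as well as the device.

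This bears on the main question. Section 2 defines feasibility as whether a device can be used in clinical practice, and sections 3 and 7 compare usable data across devices before a panel selects one for a larger trial.

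**Working it through.** **Statements side by side**

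1. Visit 1 (section 3): the device goes on the usual inhaler or needs an app.
2. INCA (section 3): Diskus only, stated outright.
3. Entry to Block 2b (section 3): age 12 or over. No other condition is given.
4. Randomisation (section 3): matched on age and group size, not inhaler type.
5. Eligibility (4.2, 4.3): any inhaled corticosteroid, with no inhaler-type criterion.

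A child aged 13 on inhaled corticosteroids from a non-Diskus inhaler, with a suitable phone, satisfies 3 to 5 and can be allocated INCA. For that child, 1 and 2 cannot both be followed. The app alternative in 1 does not help, because INCA is described only as an attachment.

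**Does any other text resolve it?**

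- The cross-reference in the Visit 1 sentence points back to the device descriptions. These give the limit but no matching rule.
- Drug history (section 5) is taken at Visit 1 and is not linked to eligibility or allocation. The screening column of Appendix 1 lists consent, eligibility criteria and demographics only.
- The clinician's freedom to give alternative treatment (8.2) is general and does not match inhalers to devices.

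**Other devices.** Flo-Tone is said to attach to an MDI. The text does not say that it fits nothing else, so exclusivity is implied only. Smartinhaler Plus compatibility is not stated in either direction.

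**Size.** The plan gives no figure on this point. Its one sample-size figure, 29 participants for 10% prevalence, 2 instances and 80% (section 7), reproduces: the exact binomial P(X ≥ 2) is 0.785 at n = 28 and 0.801 at n = 29. The present point does not affect it.

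Let q be the share of children in the age group whose usual inhaler does not fit the allocated device. The documents do not give q. With 5 children per device, and assuming independent children and no informal steering by inhaler before allocation:

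- expected mismatches = 5q
- P(at least one) = 1 − (1 − q)^5

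| q (assumed) | 5q | P(at least one of 5) |
|---|---|---|
| 0% | 0 | 0% |
| 5% | 0.25 | 1 − 0.95^5 = 23% |
| 10% | 0.5 | 1 − 0.90^5 = 41% |
| 20% | 1.0 | 1 − 0.80^5 = 67% |
| 50% | 2.5 | 1 − 0.50^5 = 97% |

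**The case against.** The best defence is that the Visit 1 sentence is a generic summary of four devices and refers back to the specific conditions, and that silence on inhaler type in 4.2 is an omission and not a contradiction. The age rule shows that the sponsor thought about the Diskus. The nurses who routinely provide the asthma devices would probably notice a poor match. The study is described as largely qualitative and exploratory, and Blocks 2a and 2b are already separated by age, so a strict randomised comparison with the mixed-age blocks was limited from the start.

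Much of this stands. The study's exploratory nature and the age split reduce the harm, and unwritten steering may occur. The reference diagram is also not available to this review, so an allocation rule shown only there cannot be ruled out. But nothing in the text turns the age rule into a Diskus rule, and informal steering would itself make allocation depend on inhaler type without any record.

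A reader might infer more: that two of the four devices each fit a single inhaler type, that some children will certainly be unable to use their device, and that the problem is confined to those two arms. The documents do not support this. Exclusivity is explicit for INCA alone, the inhaler mix is not given and q = 0 is not excluded, and the silence on Smartinhaler Plus means that Block 1 cannot be cleared.

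**Conclusion.** The concern holds for INCA. Followed as written, the plan can allocate a child of 12 or over a device that does not fit the usual inhaler, and the age rule does not prevent this. For Flo-Tone and Smartinhaler Plus, compatibility needs to be stated before the point can be settled either way.

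The certain part is structural: 5 of the 30 planned children are in a block whose device needs a Diskus, and each is one fifth of that device's evidence. How many would be affected is unknown. The probabilities above illustrate an assumed q and are not estimates for this clinic. This should be corrected before recruitment, but it does not undermine the study as a whole.

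**What to change.** - Reconcile the device descriptions and the Visit 1 sentence in section 3 with the criteria in 4.2, and state which inhalers each of the four devices fits.
- Record usual inhaler type before allocation, ahead of the drug history now taken at Visit 1.
- Apply whatever compatibility rule the sponsor adopts before randomisation, and identically to all arms within an age group. A rule applied to Blocks 2a and 2b alone would send incompatible children to Blocks 1 and 3 and make allocation depend on inhaler type.
- Keep every randomised child in the feasibility denominator for the allocated device. Count failure to fit as an outcome for that device, even if the child withdraws before the 8-week threshold in 4.4.
- Record any change of inhaler, and report results with and without those children.

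This review does not say which inhaler or switching rule is right. That is for the sponsor and the clinical team.

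The cost is amended wording, one extra screening field and possibly slower recruitment or a narrower eligible group. If the rule excludes many children, the findings will apply to fewer of the clinic's patients, and the report should say so.

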APPENDIX 1. SUMMARY OF INVESTIGATIONS, TREATMENT AND ASSESSMENTS		
	24	

GLOSSARY OF ABBREVIATIONS

KEYWORDS

Electronic monitoring device (EMD)
Novel electronic monitoring device (NEMD)
Compliance
Adherence
Children
Asthma

STUDY SUMMARY

TITLE	A feasibility study to assess novel electronic monitoring devices for monitoring adherence in children with asthma
DESIGN	A mixed method (quantitative and qualitative) open label, block randomised feasibility study
AIMS	
 1. To assess the feasibility of 4 novel electronic monitoring devices in children aged 6-16 years with asthma, in terms of usability and acceptability by patients/ guardians and healthcare professionals (qualitative study) 2. To evaluate the accuracy of these devices and assess whether they impact on asthma control (quantitative study)
OUTCOME MEASURES	
Primary outcome: Acceptability and usability of devices to participants and healthcare professional at Royal Brompton and Harefield NHS foundation Trust (RBHT)
 
Secondary outcomes:
 
 1. Accuracy of the adherence data collected from the devices. 2. Effect on asthma control as measured by asthma control test (ACT) or childhood asthma control test (cACT) score; exhaled nitric oxide (FENO), spirometry (FEV1) and bronchodilator reversibility (BDR).
POPULATION	Children aged 6-16 years with asthma on inhaled corticosteroid therapy.
ELIGIBILITY	Children aged 6-16 years with a diagnosis of asthma on inhaled corticosteroids who are being treated or followed up by the paediatric respiratory difficult asthma clinic at Royal Brompton hospital.
DURATION	Up to 16 weeks

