4. PARTICIPANT ENTRY

4.1 PRE-REGISTRATION EVALUATIONS

Children will be recruited from the outpatient clinics at the Royal Brompton Hospital

Written information regarding the study (the patient information sheet) and contact details of the study team will be given to parents

Written, informed consent from the parent / guardian and consent (if appropriate) or assent from the child will be obtained by a member of the study team prior to undertaking any study procedures. "Informed consent" requires individual discussion with the child and their parent / guardian about the study and the nature of the procedures to be conducted in a language that is easy to comprehend. The child and their parent /guardian will be given adequate time to decide whether or not they wish to participate. The child and their parent / guardian should understand that his / her refusal to participate in the study will not affect their subsequent medical care and if they do consent they may withdraw at any point without affecting their care.

The participant consent form must be signed by a member of the study team to confirm that informed consent was obtained. The original of the signed declaration of consent will be stored in the case notes. A copy will be given to the parent / guardian

Information sharing

Consent will be sought to inform the child's GP and usual hospital consultant of their enrolment in the study. If clinically important information is found as a result of the study this will be discussed with the participant and their parent / guardian and their consent sought to share this information with their GP and / or other relevant medical professionals.

Follow up of participants after study completion

At the end of the study (as a result of study completion or withdrawal) participants will continue to receive their usual clinical care.

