4.4 WITHDRAWAL CRITERIA

Children/parents/carers may withdraw any time without affecting their treatment or care.

If adherence data has been collected for > 8 weeks of treatment then permission will be requested to use this data from parents/carers. If data has not been collected for > 8 weeks then this will not be used.

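### Child and carer views, the primary outcome, are gathered only at the end of the study, and the plan makes no provision for hearing families who withdraw

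*Combined protocol and SAP*

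**What the plan says.** The Study Summary names the primary outcome as "Acceptability and usability of devices to participants and healthcare professional". Section 3 (Analysis, Qualitative) gives its source: "The focus group and one to one interviews will be used to assess the usability and acceptability of the devices". Section 2 says the same of both constructs.

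On timing, children are "asked to conduct up to 16 weeks of home monitoring using their allocated NEMD on their first visit". Visit 3 then invites participants and carers to a focus group or a "one to one interview, depending on their availability at the end of the study period". Appendix 1 ticks the focus group or interview in one column only, the last follow-up column (up to 6 months). The paediatric respiratory nurses have a separate focus group.

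On leaving the study, Section 4.4 says "Children/parents/carers may withdraw any time without affecting their treatment or care". The rest of that section concerns adherence data. With more than 8 weeks collected, permission to use the data is sought; otherwise, "If data has not been collected for > 8 weeks then this will not be used". Section 4.1 adds: "At the end of the study (as a result of study completion or withdrawal) participants will continue to receive their usual clinical care". Section 8.2 confirms that no reason need be given.

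Sections 3 and 7 both end with an expert panel that chooses one device for a larger trial, using the combined qualitative and quantitative results.

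**The concern.** Section 2 defines usability and acceptability by such things as ease of use, problems met, whether the child liked the device and whether it suited daily life. These are also plausible reasons for a family to leave. If so, the accounts most likely to be missing are among the most informative about the primary outcome.

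The study compares devices so that a panel can choose between them. If families are lost for reasons tied to the device, and to different degrees across devices, the panel compares accounts that are selected differently. The device data cannot be relied on to fill the gap, because a family that withdraws with 8 weeks of data or less also leaves the usable-data comparison. Followed as written, the plan can lose such a family from both strands of the evidence report.

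**Working it through.** **1. What reaches the panel, by type of family**

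| Family | Interview | Device data |
|---|---|---|
| Completes | Invited at Visit 3 | Used |
| Stops the device, stays enrolled | Invited at Visit 3 (the invitation is not limited to continuing users) | No exclusion stated |
| Withdraws, more than 8 weeks collected | Nothing specified | Used with permission |
| Withdraws, 8 weeks or less collected | Nothing specified | Not used |

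Other provisions do not close the gap. The calls at day 7-14 and week 6-7 check function and use and answer queries. The week 4 download checks that devices work. The nurse focus group gives the staff view. Section 8.2 keeps children in follow-up when a clinician gives alternative treatment, which is not the same as a family withdrawing.

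**2. The plan's own figure**

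Section 7 cites 29 participants for a theme of 10% prevalence, 2 instances and 80%. With P(X ≥ 2) = 1 − (1−p)^n − n·p·(1−p)^(n−1) and p = 0.10:

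- n = 28: 0.785
- n = 29: 0.801, so 29 is reproduced
- n = 30 (planned): 0.816

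The margin is one child, and no allowance for missing interviews is stated. With 27 interviewed (10% missing, assumed) the probability is 0.767; with 24 (20% missing, assumed) it is 0.708. Recruiting more children would restore the number but would not remove selection.

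**3. Weight of one withdrawal**

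Section 3 gives five children each to Flo-Tone with Rafi-tone and to INCA, and ten per block overall. One child without an interview is 1/5 = 20% of a five-child device's accounts, or 1/10 = 10% in a ten-child block.

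**4. How a complaint can drop out of sight (assumed rates)**

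Use the same criterion of two instances. Let a share p of children hold a complaint and a share w of those holders withdraw unheard, so that p(1−w) replaces p.

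- Five-child device, p = 0.40: w = 0 gives 1 − 0.6^5 − 5(0.4)(0.6^4) = 0.663. With w = 0.5 the effective share is 0.20, giving 1 − 0.8^5 − 5(0.2)(0.8^4) = 0.263.
- Ten-child block, p = 0.40: 0.954 falls to 0.624 with w = 0.5.
- All 30 children, p = 0.10: 0.816 falls to 0.447 with w = 0.5.

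**5. Direction (assumed rates)**

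Let s be the true share satisfied, u the share of satisfied families lost and w the share of dissatisfied families lost. The satisfied share among those heard is s(1−u) / [s(1−u) + (1−s)(1−w)]. With s = 0.60:

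- u = w = 0.10: 0.54/(0.54 + 0.36) = 60%, no distortion
- u = 0.10, w = 0.30: 0.54/(0.54 + 0.28) = 66%, too favourable
- u = 0.30, w = 0.10: 0.42/(0.42 + 0.36) = 54%, too unfavourable

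This share stands in for the balance of views heard. The thematic analysis does not plan to compute it. The documents give none of s, u, w or p.

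**The case against.** The plan can be defended on several counts, and most of them narrow the point.

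- A reader might infer that every child who abandons a device goes unheard. The documents do not support this: Visit 3 invites participants and carers without requiring continued use. Only withdrawal from the study is at issue.
- A reader might take the phrase about availability to mean that attendance is selective. It more naturally governs the choice between focus group and individual interview, and that choice should widen participation.
- A reader might infer that withdrawn families are barred from interview. The plan is silent. Section 4.1 even treats withdrawal as one way the study ends, so an invitation at that point is arguably open. Its sentence on usual care covers completers too, so it closes nothing.
- Troubleshooting calls and the nurse focus group may bring some problems to light second-hand. That is true, but neither is defined as a source of the child's or carer's view.
- This is a small exploratory study that looks for themes, so a percentage favourable per device is not a planned result. This stands, and it is why the size is given above in accounts and themes. The 20% also counts children only, although carers may speak as well.

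The absence of any stated step for withdrawing families remains.

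**Conclusion.** The gap is real but limited. For families who withdraw, the plan specifies no interview, no recorded reason and no count by device, and it discards their adherence data if these cover 8 weeks or less. In the two five-child groups, each such family removes one of five children's accounts of that device.

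It would go too far to say that acceptability will look best for the devices that lost their dissatisfied users. A device can look more acceptable than it is only if dissatisfied families withdraw more often than satisfied ones. A distorted comparison also needs the loss to differ between devices. The documents give no withdrawal rates, so size and direction are unknown, and the probabilities in the working are illustrations on assumed rates. The point is an inexpensive improvement to data collection. It should be settled before recruitment, because views not collected cannot be recovered at analysis.

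**What to change.** In Section 3 (Visit 3) and Section 4.4, state that any family that withdraws will be invited at that time to a short one to one interview, in person or by telephone, using the same semi-structured questions. It should be voluntary, with no obligation to give reasons, in keeping with Section 8.2. Include these transcripts in the thematic analysis. In the evidence report to the expert panel, give by device the numbers allocated, stopping use, withdrawing and interviewed, with any reasons offered.

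The cost is protocol and consent wording and a few short calls by the existing team, most of which would replace a Visit 3 interview. Some families will decline, so selection will be reduced rather than removed; the counts by device will show how much remains.
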